symptoms of CRS include fever, fatigue, headache, rash, arthralgia, and myalgia. More severe cases are characterized by hypotension that requires vasopressor treatment and/or hypoxia that requires medical intervention. They can progress to an uncontrolled systemic inflammatory response with circulatory shock, vascular leakage, disseminated intravascular coagulation, and multi–organ-system failure. Flu-like symptoms were observed during the two clinical studies with RO7020531 (NP39305 and YP39553) at 140 mg to 170 mg single or multiple QOD doses up to 6 weeks. These symptoms overlap with and are not distinguishable from mild cases of CRS.

A8.12 ENHANCED SAFETY MONITORING DURING COMBINATION TREATMENT WITH CpAM + TLR7 + NUC

Based on the emerging data from Phase 1 studies NP39305 (HV and patient cohorts) and YP39553 (single– and multiple–ascending-dose clinical study in Chinese HVs), it became evident that in all cases of flu-like symptoms, the initial onsets emerged within the initial 3 doses of RO7020531. For this reason, pre-dose laboratory analyses and optional extended in-hospital stay with frequent vital sign monitoring (every 2 to 4 hours) and ECGs (pre-dosing and 6 to 8 hours after dosing at each visit) are scheduled for the initial 3 doses of each combination cycle and guided by emerging AEs as follows:

- on Day 1 and/or Day 169 (first day of the second cycle of TLR7 dosing), participants will stay in the clinical unit for 12 hours with an option to stay in the clinic for up to 24 hours (at the Investigator's discretion) in case pyrexia and additional flu-like symptom(s) emerge and do not respond to symptomatic treatment (paracetamol/acetaminophen up to 2 g/day) during the first 12 hours post-combination dosing. For those participants who stay up to 24 hours, an additional 24 hours post-dose laboratory assessment will be done on Day 2 and Day 170, respectively.
- on Day 3 and Day 171 (third day of the second cycle of TLR7 dosing), participants
 will stay in the clinical unit for 8 hours with an option to stay in the clinic for up to 12
 hours (at the Investigator's discretion) in case pyrexia and additional flu-like
 symptom(s) emerged and would not respond to symptomatic treatment
 (paracetamol/acetaminophen up to 2 g/day) during the first 8 hours postcombination dosing.
- on Day 5 and Day 173 (fifth day of the second cycle of TLR7 dosing), participants
 will stay in the clinical unit for 8 hours with an option to stay in the clinic for up to 12

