Appendix 12 Study Details Specific to siRNA (RO7445482) + TLR7 (RO7020531) + NUC Arm

[figure not shown]
An overview of short interfering RNA (siRNA) + toll-like receptor 7 (TLR7) + nucleos(t)ide NUC treatment arm is shown in Appendix 12-Figure 1.

Participants will receive RO7445482 (also known as DCR-HBVS; 200 mg Q4W) in addition to their background NUC therapy for the 48-week treatment period. RO7020531 (150 mg once every other day [QOD]) will be administered during Weeks 13-24 and Weeks 37-48 (i.e., 2 treatment cycles of 12 weeks' duration each and 42 doses of RO7020531 for each cycle). At the end of the treatment period, participants will continue NUC treatment during the follow-up unless the NUC discontinuation criteria have been met (see Section 6.8).

Approximately 30 participants will be randomized to this treatment arm.

If a 30% delta for HBsAg loss is observed at Week 48 (EOT) or follow-up Weeks 12 or 24 (primary endpoint) the treatment arm may be expanded to accrue additional efficacy and safety data, and to contribute to Phase 3 design planning. If a successful interim analysis is observed at Weeks 12 or 24, shorter treatment duration arms (12 and 24 weeks' duration) and/or a response-guided therapy (RGT) arm may be added.

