TLRs are a family of pathogen-recognition receptors that activate the innate immune response. The stimulation of TLR7 mediates an endogenous type I IFN response, which is critical in development of a broad, effective, and protective immunity against hepatitis viruses (Horscroft et al 2012, Funk et al 2014). Compared to pegylated interferon-alfa (PEG-IFN-α) therapy, treatment with a TLR7 agonist induces broader immunomodulatory effects that are likely to lead to more effective control and functional cure of chronic HBV infection (Strader et al 2004, Isogawa et al 2005). TLR7 agonists induce the production of multiple isotypes of IFN from plasmacytoid dendritic cells (pDCs) which have been shown in vitro to possess additive or synergistic antiviral effects compared to exogenous PEG-IFN.

Non-clinical studies with RO7020531 suggest that it is rapidly converted to the active metabolite RO7011785, and data from in vivo studies with RO7020531 and in vitro studies with RO7011785 support immune activation as the mechanism of action.

To date, clinical experience with RO7020531 includes two Phase 1 clinical studies: an EIH study in HVs and CHB participants (NP39305) and a study in HVs of Chinese descent (YP39553).

A12.2 BENEFIT/RISK ASSESSMENT SPECIFIC TO SIRNA+ TLR7 + NUC ARM

The 48-week treatment with RO7445482 and RO7020531 in combination with NUC aims to result in therapeutic benefit for participants, including possibly higher functional cure rates than observed currently with standard-of-care therapies (monotherapy with NUC or PEG-IFN). The concurrent RO7445482 and RO7020531 administrations aim is to test the scientific hypothesis whether concurrent direct-acting antiviral and immunomodulatory agent combination therapy maximizes the efficacy outcomes.

Given that reduction in viral antigens is anticipated to result in functional immune recovery, the potency of an immunomodulatory agent is expected to increase if administered following a reduction in HBsAg. Consequently, in this treatment arm, the RO7020531 12-week treatment cycles will commence at week 13 and week 37 following administration of RO7445482 i.e., 'off/on' immunomodulatory treatment approach.

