- On Day 85 and/or Day 253 (first day of each cycle of TLR7 dosing), participants will stay in the clinical unit for 12 hours with an option to stay in the clinic for up to 24 hours (at the Investigator's discretion) in case pyrexia and additional flu-like symptom(s) emerge and do not respond to symptomatic treatment (paracetamol/acetaminophen up to 2 g/day) during the first 12 hours post-combination dosing. For those participants who stay up to 24 hours, an additional 24 hours post-dose laboratory assessment will be done on Day 2 and Day 170, respectively.
- On Day 87 and Day 255 (third day of each cycle of TLR7 dosing), participants will stay in the clinical unit for 8 hours with an option to stay in the clinic for up to 12 hours (at the Investigator's discretion) in case pyrexia and additional flu-like symptom(s) emerged and would not respond to symptomatic treatment (paracetamol/acetaminophen up to 2 g/day) during the first 8 hours postcombination dosing.
- On Day 89 and Day 257 (fifth day of each cycle of TLR7 dosing), participants will stay in the clinical unit for 8 hours with an option to stay in the clinic for up to 12 hours (at the Investigator's discretion) in case pyrexia and additional flu-like symptom(s) emerged during the first 8 hours and would not respond to symptomatic treatment (paracetamol/acetaminophen up to 2 g/day) during the first 8 hours postcombination dosing.

The Sponsor will promptly communicate to the Investigator any change to the proposed enhanced monitoring plan based on emerging data and interim safety evaluations. In case the prolonged hospital stay is not required but participants live far away and may need to be back on the following day, the investigator may decide to allow them to stay at a hotel nearby.

The Sponsor will provide participants a thermometer to use for temperature self-monitoring in case flu-like symptoms and pyrexia emerge. If at any time during the combination cycles (siRNA + TLR7 + NUC) participants experience flu-like symptoms with pyrexia (Grade 2 or above), it will be recommended to call the site and the PI or the medical personnel on site:

- may recommend participants visit the clinic for an unscheduled visit according to the SOA in Appendix 12.
- may recommend symptomatic treatment with paracetamol/ acetaminophen up to 2 g/day.

Appendix 12-Figure 2. Safety Monitoring and RO7020531 Dosing Interruption for Flu-like Symptoms and Cytopenia during Combination Treatment with siRNA + TLR7 + NUC

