- RBR = Research Biosample Repository; RNA = ribonucleic acid; siRNA= short interfering ribonucleic acid; TLR = toll-like receptor; Total HBsAg = post-dissociation of HBsAg/HBsAb complexes/components of HBsAg; VB/VR = virological breakthrough/relapse; UV = unscheduled visit.
- ^a Full physical examination at screening and at the end-of-treatment. Limited symptom-directed physical examination at other visits and as clinically indicated. Height at screening only. Weight at screening, Day 1, and Weeks 13, 25, 37, and 49. Eye examination (including fundoscopy) only at screening.
- ^b Blood pressure, pulse rate, respiratory rate and body temperature obtained at least 5 minutes after participant has been in supine/sitting position. Orthostatic hypotension test only at screening. Vital signs assessments on Days 85 and 253: predose, 2-4 hours, 4-6 hours, 6-8 hours and 8-12 hours; Vital signs assessments on day of the second and third RO7020531 dose of the first cycle, on the first day of those switching to QW dosing, and on the days of the second and third RO7020531 dose in the second cycle: predose, 2-4 hours, 4-6 hours, 6-8 hours (and 8-12 hours optional in case of extended in-clinic stay).
- ^c Historical liver biopsy or transient elastography/ARFI/MR/2D- shear wave elastography [2D-SWE] results obtained within 6 months prior to randomization are also acceptable. During screening transient elastography/ARFI/MR/2D-SWE are acceptable.
- ^d Autoantibodies refer to ANA, AMA, ASMA, and a-TPO.
- ^e Alcohol and drugs of abuse screen to be conducted according to local procedures.
- ^f Pregnancy testing for females of childbearing potential only; serum test at screening, urine test at other visits. If urine test is positive, it must be confirmed by a serum test.
- ⁹ HbA1c should be included in hematology, and is required only at screening.
- h If not collected at Day 1, samples for clinical genotyping and HBV RNA sequencing can be collected at any subsequent time point. The sample for HBV RNA sequencing aims at determining the HBV genotype. The HBV genotype may also be inferred using alternative approaches, such as serovariant determination.
- ⁱ Total HBsAg refers to HBsAg measured post-dissociation of HBsAg/HBsAb complexes/components of HBsAg.
- ^j HBV DNA sequencing will be collected in case of virological breakthrough/relapse, blood sample to be collected up to 6 times.

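### In the siRNA + TLR7 arm, the conditional 24-hour post-dose laboratory test is placed on Days 2 and 170, while the TLR7 cycles start on Days 85 and 253

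*Protocol*

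**What the plan says.** In the opening of Protocol Appendix 12, TLR7 (RO7020531) "will be administered during Weeks 13-24 and Weeks 37-48". The benefit/risk text in A12.2 agrees: "the RO7020531 12-week treatment cycles will commence at week 13 and week 37".

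A12.12 then sets enhanced monitoring for the first three TLR7 doses of each cycle. Its first bullet fixes the in-clinic stay: "On Day 85 and/or Day 253 (first day of each cycle of TLR7 dosing), participants will" stay for 12 hours, extendable to 24 at the investigator's discretion if pyrexia and other flu-like symptoms do not respond to symptomatic treatment. The laboratory test applies only to that extended group ("For those participants who stay up to 24 hours"), and for them "an additional 24 hours post-dose laboratory assessment will be done on Day 2 and Day 170, respectively".

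The second bullet continues from the Day 85/253 start ("On Day 87 and Day 255 (third day of each cycle of TLR7 dosing"), and the third uses Days 89 and 257. Footnote b of Appendix 12-Table 4 does the same: "Vital signs assessments on Days 85 and 253: predose, 2-4 hours".

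Appendix 8, A8.12, covers the CpAM + TLR7 arm. It carries the same laboratory sentence with the same two days, but there the stay is "on Day 1 and/or Day 169 (first day of the second cycle of TLR7 dosing), participants will" kept in clinic.

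**The concern.** The bullet ties a test defined by its distance from a dose to study days on which that dose has not just been given. Day 2 comes before any TLR7 exposure in this arm. Day 170 is 24 hours after the first dose of neither cycle.

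This is an operative safety instruction in an arm that Appendix 6-Table 1 lists as ongoing. Protocol Section 9.2 allows up to 30 additional participants per arm, so first TLR7 doses may still lie ahead. The participants concerned are those kept in clinic because symptoms have not settled. A12.11 says that flu-like symptoms cannot be told apart from mild cytokine release syndrome, and that haematological abnormalities in Phase 1 mostly reversed within 24 to 48 hours. A12.13 uses persistence of Grade 3 haematological abnormalities beyond 48 hours as a dose-modification trigger. A 24-hour value that is missed or mistimed would leave a gap between the dosing-day sample and the +2-day sample.

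**Working it through.** This is day arithmetic. The first day of week w is 7(w − 1) + 1, and 24 hours post-dose is the dose day plus 1.

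**Step 1: where the stated days fit.** With the Appendix 8 dosing days:
- 1 + 1 = 2
- 169 + 1 = 170

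The stated Days 2 and 170 are reproduced exactly for the CpAM + TLR7 arm.

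**Step 2: cycle starts in Appendix 12.** With Weeks 13 and 37:
- 7 × 12 + 1 = 85
- 7 × 36 + 1 = 253

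These match the days named in A12.12 and in footnote b of Appendix 12-Table 4, so the arm's dosing days are consistent across those places.

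**Step 3: 24 hours after those doses, against the stated days.**

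| | Cycle 1 | Cycle 2 |
|---|---|---|
| First TLR7 dose (A12.12) | Day 85 | Day 253 |
| Dose day + 1 | Day 86 | Day 254 |
| Stated laboratory day | Day 2 | Day 170 |
| Gap to dose day | 85 − 2 = 83 | 253 − 170 = 83 |
| Gap to 24-hour point | 86 − 2 = 84 | 254 − 170 = 84 |

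**Step 4: visit windows.** Appendix 12-Table 4 allows ±1 day at Day 85. At Day 253 it allows ±2 days on its first page and ±3 on the continuation pages. The 24-hour point then falls within Days 85 to 87 for the first cycle, and within Days 252 to 256 (±2) or 251 to 257 (±3) for the second. Days 2 and 170 lie outside every range.

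**Step 5: where Day 170 falls.** Weeks 13 to 24 are Days 85 to 168. The 42nd every-other-day dose of the first cycle is nominally on Day 85 + 2 × 41 = Day 167. Day 170 therefore sits between the cycles. A12.13 describes the cycles for participants on weekly dosing as Weeks 13 to 25 and 37 to 49, which would blur the end of the first cycle. Even so, Day 170 is 170 − 85 = 85 days after the first dose of that cycle, so the conclusion does not change.

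**Step 6: what the schedule settles.** Appendix 12-Table 4 has no column for Day 2, 86, 170 or 254. It schedules haematology, chemistry, coagulation, GLDH and urinalysis on Days 85 and 253 and at the two following +2-day visits of each cycle.

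**The case against.** The strongest answer is that the slip is visible and hard to act on. A participant held on Day 85 is already past Day 2, and one held on Day 253 is already past Day 170, so the printed days cannot be carried out. The description of the test as 24 hours post-dose still tells the site when to sample. Full laboratory tests follow about 48 hours after the first dose. Unscheduled visits are available, and Section 8.2.5 permits extra samples when symptoms call for them. The participants are under observation in the clinic. All of this stands. It limits the harm but does not remove the contradiction.

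A second answer is that siRNA is given on Days 1 and 169 in this arm, so Days 2 and 170 might be meant as 24 hours after siRNA. That does not work. The sentence pairs its two days with the Day 85 and Day 253 stays, A12.12 sets no stay on the siRNA-only days, and the section is justified by experience with the first TLR7 doses.

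A reader might infer more than the documents support:
- **That the test will be missed.** The post-dose wording may still guide sites, so the documents support only that it could be missed or mistimed.
- **That this sentence is the only instruction.** Appendix 12-Figure 2 covers safety monitoring for flu-like symptoms and cytopenia, and its content is not visible here. The absent column also proves little: Appendix 8-Table 4 has no Day 2 or Day 170 column either, although the days fit there.
- **That the test exists to detect cytopenia or cytokine effects.** No passage states its purpose, and the cytokine and ISG panels are specified pre-dose and 6 hours post-dose.
- **That the sentence was certainly copied from Appendix 8.** The identical wording points that way. So does Appendix 12-Table 3, whose reference column still cites Appendix 8 alongside Section A12.12. It remains an inference.

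**Conclusion.** The inconsistency is real and lies within one bullet. Days 2 and 170 cannot be 24 hours after doses given on Days 85 and 253. They are 83 days before the dose days and 84 days before the 24-hour points, in both cycles. The conclusion assumes only that the two laboratory days are paired in order with the two stays named in the same bullet.

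The reach is narrow: participants in the siRNA + TLR7 arm who are kept in clinic for the extended stay. The scheduled laboratory tests and vital signs on the first three dosing days are unaffected, as are the primary endpoint, sample size and analyses. This is a drafting inconsistency in a safety-monitoring instruction. It should be corrected because the arm is ongoing and the schedule does not resolve the day.

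**What to change.** Reconcile the stated laboratory days in A12.12 with the TLR7 cycle start days in the same bullet and with Appendix 12-Table 4. Check Appendix 12-Figure 2 for consistency at the same time. Which clinical timing applies is for the sponsor to decide and state. The cost is one line in Appendix 12; no analysis or sample-size text changes.

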Any clinically-significant AEs or laboratory abnormalities that in the opinion of Investigator may be related to NME(s)	Interrupt NME(s) until AEs/laboratory abnormalities are resolved. Re-introduce NME(s) (on a case-by case basis, which may be at a modified dose if deemed necessary)	
Any medical condition or AE/laboratory abnormalities that the lnvestigator or Sponsor determines may jeopardize the participant's safety if he or she continues in the study		Section 7.1
Sponsor or Investigator determination that treatment discontinuation is the best interest for the participant	Discontinue NMEs, continue NUC	
Pregnancy		
CHB disease progression		

Every effort should be made to obtain information on participants who withdraw from the treatment but have not withdrawn from the study. Participants who permanently discontinue study treatment will be asked to return to the clinic for an unscheduled/early

termination visit and will undergo follow-up assessments. The primary reason for premature study treatment discontinuation should be documented on the appropriate eCRF.

Participants, who permanently discontinue study treatment as part of an early termination of a treatment arm due to Sponsor's decision, will undergo safety follow-up assessments as described in Appendix 6. For participants who are in treatment arms NOT terminated by the sponsor, will proceed as planned and undergo follow up as per the SOA of the respective treatment arm.

Participants who discontinue study treatment due to non-safety reasons may be replaced.

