8.3.3 Follow-Up of Adverse Events and Serious Adverse Events 8.3.3.1 Investigator Follow-Up

The Investigator should follow each adverse event until the event has resolved to baseline grade or better, the event is assessed as stable by the Investigator, the event is otherwise explained, the participant is lost to follow-up (see Section 7.3), or the participant withdraws consent. Every effort should be made to follow all serious adverse events considered to be related to study treatment or study-related procedures until a final outcome can be reported.

During the study period, resolution of adverse events (with dates) should be documented on the Adverse Event eCRF and in the participant's medical record to facilitate source data verification. If, after follow-up, return to baseline status or stabilization cannot be established, an explanation should be recorded on the Adverse Event eCRF.

All pregnancies reported during the study should be followed until pregnancy outcome and reported according to the instructions provided in Section 8.3.5.

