3.1. ASSESSMENT OF SEVERITY

The terms "severe" and "serious" are not synonymous. Severity refers to the intensity of an adverse event (according to pre-defined Division of AIDS Table for Grading the Severity of Adult and Pediatric Adverse Events [DAIDS] criteria); the event itself may be of relatively minor medical significance (such as severe headache without any further findings).

Severity and seriousness need to be independently assessed for each adverse event recorded on the eCRF.

Serious adverse events are required to be reported by the Investigator to the Sponsor immediately (i.e., no more than 24 hours after learning of the event).

The adverse event severity grading scale for the DAIDS (v2.1) will be used for assessing severity for adverse events (see Appendix 2-Table 1).

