TLR7 agonist activates innate and adaptive immune responses, and these mechanisms include induction of type I interferon (IFNα). Safety data from the ongoing Phase 1 studies showed IFN-related flu-like symptoms (headache, pyrexia, chills, myalgia, nausea), mostly of mild intensity; and in some participants, hematological abnormalities (e.g., neutropenia, lymphopenia). During the two clinical studies with RO7020531 (NP39305 and YP39553), all hematological abnormalities were asymptomatic and in most cases reversible within 24 to 48 hours.

TLR7 agonists as a class may have the potential, in a dose-dependent manner, to lead to hypotension and distributive shock due to excessive cytokine release (cytokine release syndrome [CRS])—e.g., IL-1,IL-6,IL-10, IFN-γ, TNF-α etc.—by immune activation. CRS can present with a variety of symptoms, from mild symptoms overlapping with mild flu-like symptoms to severe or life-threatening manifestations. Mild symptoms of CRS include fever, fatigue, headache, rash, arthralgia, and myalgia. More severe cases are characterized by hypotension that requires vasopressor treatment and/or hypoxia that requires medical intervention. They can progress to an uncontrolled systemic inflammatory response with circulatory shock, vascular leakage, disseminated intravascular coagulation, and multi–organ-system failure. Flu-like symptoms were observed during the two clinical studies with RO7020531 (NP39305 and YP39553) at 140 mg to 170 mg single or multiple QOD doses up to 6 weeks. These symptoms overlap with and are not distinguishable from mild cases of CRS.

A12.12 ENHANCED SAFETY MONITORING DURING COMBINATION TREATMENT WITH SIRNA + TLR7 + NUC ARM

Based on the emerging data from Phase 1 studies NP39305 (HV and patient cohorts) and YP39553 (single– and multiple–ascending-dose clinical study in Chinese HVs), it became evident that in all cases of flu-like symptoms, the initial onsets emerged within the initial 3 doses of RO7020531. For this reason, pre-dose laboratory analyses and optional extended in-hospital stay with frequent vital sign monitoring (every 2 to 4 hours) and ECGs (pre-dosing and 6 to 8 hours after dosing at each visit) are scheduled for the initial 3 doses of each combination cycle and guided by emerging AEs as follows:

[figure not shown]

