*Based either on central laboratory (as per the SoA in Appendix 12) and/or local laboratory if performed for participant management and/or decision-making. In such a scenario, if local laboratory tests are performed, an additional sample will be sent to the central laboratory, but decisions will be based on local laboratory results.

A12.13 DOSE MODIFICATION

Dose reduction to 100 mg QOD with RO7020531 for intolerability associated with adverse events should be considered by the Investigator during the treatment phase in the following situations:

- Grade 3 (severe) TLR7 agonist-related AEs of flu-like symptoms that persist > 24 hours despite prophylactic and/or symptomatic treatment with acetaminophen (paracetamol)
- Grade 3 (severe) hematological (e.g., cytopenia) laboratory abnormalities that persist for > 48 hours
- TLR7 agonist-related SAE
- Flu-like symptoms that are not tolerated

In the above situations, RO7020531 150 mg QOD dosing should be interrupted until AEs, laboratory abnormalities, or SAEs improve to Grade 1 or less, before initiating a dose reduction to RO7020531 100 mg QOD.

For repetitive/recurrent flu-like symptoms/pyrexia (either responsive or unresponsive despite symptomatic treatment with acetaminophen or poorly manageable despite prophylactic treatment with acetaminophen) or other TLR7 agonist-related AEs (including repetitive AEs) which are not well manageable, the Investigator in discussion with the participant should consider a RO7020531 dose reduction to 100 mg QOD. The Medical Monitor is available to the PI to answer any medical questions.

Following the RO7020531 dose reduction to 100 mg QOD, the Investigator should interrupt RO7020531 dosing if any of the following situations occur:

- Grade 3 (severe) TLR7 agonist-related AEs of flu-like symptoms that persist for > 24 hours despite prophylactic and/or symptomatic treatment with acetaminophen (paracetamol)
- Grade 3 (severe) hematological (e.g., cytopenia) laboratory abnormalities that persist for > 48 hours
- TLR7 agonist-related SAE

Following the RO7020531 dose reduction to 100 mg QOD, if flu-like symptoms are still not tolerated by the participants, a reduction of the dosing frequency of RO7020531 to 100 mg QW (once a week) should be considered.

Appendix 12-Table 3 summarizes the dose interruption/modification/discontinuation guidelines for the siRNA+TLR7+NUC combination arm.

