Appendix 12-Table 3. Dose Interruption/Modification/Discontinuation Guidelines for the siRNA+TLR7+NUC Combination Arm

Laboratory/Clinical Parameters	Recommendation	Reference
TLR7-related AEs		
Grade 3 flu-like symptoms >24 hr despite prophylactic and/or symptomatic treatment, or, repetitive flu-like symptoms that are poorly tolerated	Interrupt RO7020531 dosing (150 mg QOD). Reduce RO7020531 to 100 mg QOD when AEs improved to Grade 1 or SAE resolved. Following dose reduction (100 mg QOD), if similar Grade 3 AEs or laboratory	
Grade 3 hematological abnormalities that persist >48 hr	abnormalities occur, interrupt RO7020531. In general, consider switching to 100 mg QW (at least 5 days	Appendix 8 (Section A12.12)
TLR7 agonist-related SAE	after the last dose) prior to drug discontinuation (case- by-case basis).	
siRNA-related AEs		
No laboratory or clinical parameters have been identified yet	No dose modification recommendations for siRNA	N/A
General criteria for dose interruptions/discontinuations for	or all NMEs	
Liver transaminases and liver function test	See Section 7.1	Section 8.3.8.3
Confirmed virological breakthrough	Discontinue NMEs and continue treatment according to local standards	Section 8.3.8.1
Others	See Section 7.1	

In general, when addressing tolerability issues with RO7020531, prior to the investigator making a decision to discontinue study treatment or participant withdrawal of consent from study treatment, a dose reduction should be discussed and evaluated if considered in the participant's best interest. The Medical Monitor is available to the Investigator to answer any medical questions.

The first dose of RO7020531 100 mg QOD should be administered in the clinic, and participants should be monitored for at least 8 hours as per SoA (with pre-dose safety laboratory assessment, every 2 to 4 hours for vital signs, and ECG assessment at pre-dose and 6 to 8 hours post-dose). This first visit should be synchronized with the participant's current RO7020531 QOD dosing schedule.

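### In the ongoing siRNA + TLR7 arm, the A12.13 text and its summary table give different recovery conditions for restarting RO7020531 after a TLR7-related SAE

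*Protocol*

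**What the plan says.** A12.13 lists a TLR7 agonist-related SAE among the situations in which RO7020531 should be considered for reduction from 150 mg to 100 mg QOD. For all of these situations it sets one recovery threshold: "RO7020531 150 mg QOD dosing should be interrupted until AEs, laboratory abnormalities, or SAEs improve to Grade 1 or less".

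A12.13 then introduces the table: "Appendix 12-Table 3 summarizes the dose interruption/modification/discontinuation guidelines". That table gives TLR7 agonist-related SAEs their own row and splits the threshold in two: "Reduce RO7020531 to 100 mg QOD when AEs improved to Grade 1 or SAE resolved".

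Three other statements bear on the reading. Appendix 2, Section 3.1 says "Severity and seriousness need to be independently assessed for each adverse event", so an event can be serious and Grade 1 at the same time. Section 8.3.3.1 asks investigators to follow each event "until the event has resolved to baseline grade or better", among other stopping points. The general table in Section 7.1 says "Interrupt NME(s) until AEs/laboratory abnormalities are resolved".

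For the first 100 mg QOD dose, A12.13 requires at least 8 hours of in-clinic observation with vital signs every 2 to 4 hours, and refers to the SoA. In Appendix 12-Table 4 the 100 mg QOD column has vital signs marked. Footnotes t and u name that dose for ECGs and for in-clinic administration. Footnote b, which sets the vital-sign times, names the first three doses of each cycle and the first day of a switch to QW, but not this dose.

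**The concern.** The restart rule decides when a participant who has had a drug-related SAE is exposed to the drug again. If the text and its summary table differ, two sites can follow the protocol and restart in different clinical states, and a monitor cannot say which of them deviated. Site staff often work from the summary table, so the difference could matter in practice. A12.11 describes hypotension and distributive shock as possible dose-dependent class effects, so the condition for re-exposure should not be ambiguous.

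The footnote matters less. A site that builds the first 100 mg QOD visit from the SoA alone finds vital signs marked but no times for them.

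**Working it through.** The main check is a comparison of wording. Let *g* be the current grade of a TLR7-related SAE and *b* its grade at baseline (0 if absent).

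- A12.13 text: restart allowed if g ≤ 1.
- Table 3: restart allowed if the SAE has resolved. The protocol does not define the word for this purpose. The nearest wording is the follow-up rule in Section 8.3.3.1, which would make the condition g ≤ b.

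| Baseline b | Current g | A12.13 text | Table 3, resolved read as g ≤ b |
|---|---|---|---|
| 0 | 0 | restart | restart |
| 0 | 1 | restart | **no restart** |
| 1 | 1 | restart | restart |
| 2 | 1 | restart | restart |
| 2 | 2 | **no restart** | restart |

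If resolved instead means that the event is over, every SAE ongoing at Grade 1 falls in the gap, whatever its baseline grade. On the baseline reading the gap runs both ways: the table is stricter when b = 0 and looser when b is 2 or more. The second case can arise because Appendix 2 counts the exacerbation of a pre-existing condition as an AE. The condition that meets both rules on the baseline reading is g ≤ min(1, b).

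**Cost of a longer wait.** Appendix 12 gives "42 doses of RO7020531 for each cycle", which is reproduced by 12 weeks × 7 days = 84 days, and 84 / 2 = 42. An extra wait of *d* days costs d / 2 doses, or d / 2 / 42 of a cycle, if missed doses are not made up. The waits below are assumptions, because the documents give no recovery times for SAEs.

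- d = 2: 1 dose, 1 / 42 = 2.4%
- d = 7: 3.5 doses, 3.5 / 42 = 8.3%
- d = 14: 7 doses, 7 / 42 = 16.7%

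For scale only, A12.11 describes Phase 1 hematological abnormalities as "in most cases reversible within 24 to 48 hours", which is about 1 dose. Those were asymptomatic and are not described as SAEs.

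**Vital-sign windows.** Footnote b already uses pre-dose, 2-4, 4-6 and 6-8 hours for second and third doses. The largest possible interval between successive readings is 4 − 0 = 4, 6 − 2 = 4 and 8 − 4 = 4 hours. At window midpoints (0, 3, 5, 7) the intervals are 3, 2 and 2 hours. The same windows at the first 100 mg QOD dose would stay within the 4-hour upper limit in A12.13.

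**The case against.** The strongest defence of the wording has four parts.

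First, the table's two limbs are joined by *or*, so an SAE at Grade 1 might be said to meet the AE limb. That would leave the SAE limb with no function, in a table that gives SAEs their own row. This part does not stand.

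Second, the general table in Section 7.1 might be thought to settle the matter for the stricter word. It does not. It covers ordinary AEs as well, and for those both A12.13 and Table 3 accept Grade 1, so the arm appendix has already departed from it. Section 6.6 also sends dose interruption to the arm appendices.

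Third, dose reduction is a matter for the investigator's consideration, with the Medical Monitor available, and few participants can be affected. This stands. It limits the size of the problem but does not say which rule applies.

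Fourth, Appendix 12-Figure 2 in A12.12, to which the Table 3 reference cell points, also deals with interruption of RO7020531, and its content is not readable here. This stands as a limit on the review. The figure's title concerns flu-like symptoms and cytopenia, so it may not address SAEs.

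Three stronger conclusions are tempting, and the documents do not support them.

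- A reader might infer that monitoring is missing at the first 100 mg QOD dose. A12.13 sets it out in workable form and Table 4 marks vital signs for the visit. Only the footnote is out of line.
- A reader might infer that adopting the table's wording alone would satisfy both rules. The row with b = 2 and g = 2 shows that it could remove the Grade 1 ceiling.
- A reader might infer an effect on the primary analysis. SAP Table 5 handles dose and frequency switching by treatment policy, SAP Section 4.1 bases evaluability on siRNA doses, and the arm's estimand in SAP Appendix 3 already includes 100 mg QOD and 100 mg QW.

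**Conclusion.** The conflict in the restart rule is real and should be corrected, because it governs re-exposure after a drug-related SAE in an ongoing arm. It reaches participants whose SAE is ongoing at Grade 1. On the reading of resolution as return to baseline, the Grade 1 case narrows to events with baseline Grade 0, and SAEs that worsened a condition of baseline Grade 2 or more are added. The arm has about 30 participants and no SAE rate is given, so the number affected cannot be estimated.

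The vital-sign footnote is a minor alignment of the schedule with the text. The Table 3 reference cell is clerical: it cites Appendix 8 with an Appendix 12 section number, while the matching cell in Appendix 8 cites its own section. Appendix 8 carries the same restart mismatch, but that arm is terminated.

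The conclusion rests on the readable text and assumes that Appendix 12-Figure 2 does not state a governing SAE rule.

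**What to change.** - **Restart rule.** State one condition in both A12.13 and Appendix 12-Table 3 that meets both rules, for example: *SAE resolved (to baseline or better) and Grade 1 or less*. Check that Appendix 12-Figure 2 agrees.
- **Schedule.** In Appendix 12-Table 4 footnote b, add the first 100 mg QOD dose with pre-dose, 2-4, 4-6 and 6-8 hour vital signs. Leave the existing QW entry as it is.
- **Clerical.** In the Table 3 reference cell, change the appendix number from 8 to 12 and keep the section number.

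These are one-line edits, suitable for a clarification letter or the next amendment. They add no procedure, because A12.13 already requires the monitoring. The participant-level cost is a possibly longer interruption: about 1 of 42 doses per 2 extra days, for those who would otherwise have restarted earlier. A participant whose baseline grade is 2 or more would have to improve beyond baseline to restart, which the A12.13 text already requires. If the medical team considers that too strict, it should say so in both places.
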